4.0 SUBJECT SELECTION

4.1 INCLUSION CRITERIA

Subject eligibility should be reviewed and documented by an appropriately qualified member of the Principal Investigator's (PI's) study team before participants are included in the study.

1. Successful completion of Study TTP488-301 through the Month 18 Visit without ongoing SAEs or history of serious adverse drug reactions during study TTP488-301.
2. Patients must enroll in the present study within 7 days of completion of study TTP488-301.
3. Evidence of a personally signed and dated informed consent document indicating that the subject (or a legally authorized representative) and caregiver/informant has been informed of all pertinent aspects of the study. Participants must be able to provide assent (where this is in accordance with local laws, regulations and ethics committee policy) and assent may be re-evaluated during the study at regular intervals.
4. Participants and caregiver/informants who are willing and able to comply with scheduled visits, treatment plan, laboratory tests, and other study procedures.
5. The subject must have a reliable caregiver/informant with regular contact (i.e., 10 hours a week as a combination of face-to-face visits and telephone contacts are acceptable) who will facilitate the subject's full participation in the study. Caregivers/informant must have sufficient subject interaction to be able to provide meaningful input into the rating scales administered in this study where caregiver/informant input is required, in particular the CDR and evidence of this should be documented in source documentation. Participants who reside in assisted living facilities are permitted provided that they meet caregiver/informant criteria.
6. Participants and caregiver/informants must be able to read, write, and speak the language in which psychometric tests are provided with visual and auditory acuity (corrected) sufficient to allow for accurate psychometric testing.

7. Subject must be able to ingest oral medications.

4.2 EXCLUSION CRITERIA

Participants presenting with any of the following will be excluded from participation in the study.

1. The subject is felt by the investigator to be unsuitable (on the basis of health, compliance, caregiver availability, or for any other reason) for inclusion in the study.
2. Subjects with serious suicide risk. If there are “yes” answers on items 4, 5 or on any behavioral question of the C-SSRS, a suicide risk assessment must be done by a qualified mental health professional with expertise in the evaluation of suicidality in the elderly (e.g., psychiatrist, geriatrician or neurologist specializing in treatment of patients with AD) to determine whether it is safe for the subject to participate in the study.
3. Subjects demonstrating a QTcF > 480 msec or a >45 msec increase from the TTP488-301 Baseline value based on the locally read ECG performed at the TTP488-301 Month 18 Visit (TTP488-303 Baseline). Participants with known history of bundle branch block (either right or left) are allowed if absolute QTcF value does not exceed 500 msec. Participants with a functioning pacemaker, indicated by an ECG displaying paced rhythm, are allowed with no QTc upper limit.
4. Other acute or chronic medical or psychiatric condition or laboratory abnormality that may increase the risk associated with study participation or investigational product administration or may prevent the subject from completing the 2-year study or may interfere with the interpretation of study results and, in the judgment of the investigator, would make the subject inappropriate for entry into this trial.

4.3 CONTRACEPTION REQUIREMENTS AND STUDY PARTICIPANT INSTRUCTION

4.3.1 Males

A fertile male study participant, whose sexual partner(s) is female and of childbearing potential, must agree to use one of the following methods of

contraception for the duration of the study (from the first dose until 90 days after the final dose of the study medication): abstinence, use of condom plus their female partners must use another form of contraception including implants, injectables, combined oral contraceptives, barrier contraception methods, spermicides, intrauterine devices (IUDs), transdermal contraceptives, and intravaginal contraception rings. The male study participant should also agree to no sperm donation for 90 days after the final dose of study medication.

At appropriate study visits, all study participants are reminded of contraception requirements as described above. Upon discharge from the study, subjects will be instructed to notify the Study Site if a female study participant or female partner of a male study participant becomes pregnant within 90 days of last dose of study medication.

5.0 STUDY TREATMENTS

5.1 RANDOMIZATION TO STUDY TREATMENT

TTP488-303 is not a randomized study. All eligible subjects will receive azeliragon 5 mg / day.

5.2 BREAKING THE BLIND

TTP488-303 is an open label study.

5.3 DRUG SUPPLIES

Drug supplies will consist of a 5 mg azeliragon supplied as a Size 2 hard gelatin capsule. The recommended storage condition for the product is room temperature at 15°C to 30°C (59°F to 86°F).

5.3.1 Formulation and Packaging

Azeliragon will be packaged into child-resistant, high density polyethylene (HDPE) bottles with heat induction seal (HIS) closures.

Storage conditions and participant dosing instructions will be listed on the packaging.

5.3.2 Administration

Treatment will begin in the clinic at the baseline visit following confirmation of eligibility. One capsule will be administered with a glass of water. Participants will be instructed to take one capsule per day by mouth for the duration of the treatment period. The day's dose of azeliragon will be administered in the clinic at each subsequent study visit. Azeliragon may be administered without regard to meals.

5.3.3 Compliance

Participants will bring all unused azeliragon capsules to each study visit. The number of capsules will be counted and documented. If more than expected are returned, participants will

be asked to account for missed doses. If the number of capsules is less than expected, participants will be asked to account for the missing capsules (e.g., capsules that are lost vs. excessive dosing of study medication). Caregivers/Informants will be instructed to assist with monitoring dosing compliance.

5.4 DRUG STORAGE AND DRUG ACCOUNTABILITY

Study drug supplies must be stored at room temperature (15°C –30°C [59°F-86°F]) in a secure and locked area. The pharmacist or designee at the study site will manage and store the study drug.

Study drugs will be accounted for in the case report form and drug accountability inventory forms as instructed by the Sponsor. At the end of the study, all drug supplies not dispensed or unused by the participants must be returned to the location designated by the Sponsor.

5.5 CONCOMITANT MEDICATION(S)

Concomitant medications and over the counter medications and supplements taken during the study must be recorded with indication, daily dose, and start and stop dates of administration. All participants will be questioned about concomitant medication and supplements at each clinic visit.

Participants must be on a stable dose of background cholinesterase inhibitor and/or memantine. Any change in dose or frequency must be captured in the eCRF.

All Medications taken after the first dose of study medication in the open label extension must be documented as concomitant medications.

Medications that may negatively affect cognitive function (e.g., antidepressants, sedatives/anxiolytics) must be at a stable dose (i.e., in the investigators judgment, efficacy and tolerability have been optimized) and are expected to continue on a stable dose for the duration of the trial. (Dose adjustments are permitted however participants should be on a stable dose at least one week prior to any protocol-specified clinical assessments). Exceptions to medications that may negatively affect cognitive function are as follows:

- Considerations for use of medications that may affect the CNS or cognition following enrollment in the open label extension. When there is an acute need for use of a medication that may negatively affect cognition or the CNS in general (e.g., sedatives/anxiolytics, antipsychotics, opiates), their use should be transient (no more than 4 weeks), must be stable for at least one week prior to any cognitive assessments, and discussed with the sponsor's medical monitor prior to use (or as soon as possible following discovery of their use). Should their use be deemed to be chronic (spanning months), discussion with the Sponsor's medical monitor is required.

The use of following concomitant medications is not allowed:

- Drugs known to be potent CYP2C8 or any other prohibited concomitant drugs (See [APPENDIX 1](#)

[PROHIBITED MEDICATION LIST](#) for a partial list).

- Any use of steroid treatment. Allowable exceptions: a) topical, otic, nasal or inhaled corticosteroid applications to the skin, and b) localized corticosteroid injections, no more than once every 6 months.
- Prescription medical food (i.e. Axona) intended for the dietary management of the metabolic processes associated with Alzheimer's disease.

No other investigational therapies for Alzheimer's disease that are being investigated for possible disease modification activity (e.g., passive immunotherapies and secretase inhibitors) or non-disease modifying purposes are allowed during this study.

During the study, participants should be instructed to review new prescriptions and over-the-counter preparations with the investigator prior to taking any medications.

All medications should be approved by the investigator prior to use and recorded on the Case Report Form (CRF). If the medication is started because of an adverse event (AE), this event should be reported on the appropriate CRF.

Any additional questions regarding medications should be addressed to the Sponsor's medical monitor.

6.0 STUDY PROCEDURES

- Study participants should consume a meal or snack prior to their clinic visit. Upon arrival, the Site staff will confirm the subject has consumed a meal or snack prior to beginning study procedures. The time of the finishing the meal/snack will be documented in the source documents. Thus clinical laboratories will be obtained under non-fasting conditions at all visits.
- Cognitive/functional assessments (in particular the ADAS-cog, MMSE and CDR-sb) should be performed as first procedures during a study visit.
- It is recommended that cognitive/functional assessments should be performed in the following order: ADAS-cog, MMSE, CDR when administered on the same day. The same rater should follow a particular subject for any given assessment for the duration of the study whenever possible. Note, the initial rating scales should be the ADAS-cog to minimize subject fatigue, followed by the MMSE. Additionally, to avoid subject fatigue, the CDR may be performed on a separate proximal visit day than the other cognitive tests. If it is to be done the same day, then the CDR should follow the MMSE as above.
- Following completion of the cognitive/functional assessments the remainder of study visit procedures will be completed.
- ECGs: obtain prior to blood sampling.
- Vital signs: obtain prior to blood sampling.
- Blood sampling should be the last procedure performed prior to dosing during a study visit.
- Dosing should occur in the clinic on study visit days.

6.1 STUDY PERIOD

6.1.1 Baseline (Month 18 of TTP488-301)

Following completion of the TTP488-301 Month 18 Visit procedures, the investigator (or an appropriate delegate at the investigator site) will obtain informed consent from each subject, caregiver/informant, and where appropriate, legally authorized representative in accordance with Subject Information and Informed Consent/Assent (where this is in accordance with local laws, regulations and ethics committee policy).

After obtaining consent, the following baseline activities will be completed.

- Review of inclusion and exclusion criteria
- If eligible, registration for the TTP488-303 study
- Dispense study drug if eligible.
- Subject begins taking study medication in the clinic as soon as baseline procedures are completed.

The TTP488-301 Month 18 assessments will also serve as the Baseline assessments for the TTP488-303 Open Label Extension. The visit procedures that are unique to the TTP488-303 baseline visit can be completed up to 7 days following the Month 18 visit for the TTP488-301 study. The 7 day window will begin on the TTP488-301 Month 18 visit day. To participate in TTP488-303, the subject must be registered and study drug is administered within 7 days of the TTP488-301 Month 18 visit day.

If it is necessary to extend the 7 day period for any other reason (e.g., schedule conflicts, patient/caregiver/informant illness, inclement weather) the Sponsor should be contacted for approval and the visit window may be extended up to 7 days. In this case, re-review of the inclusion/exclusion criteria and concomitant medications should occur to ensure that the patient continues to be appropriate for the study.

6.1.2 Month 3 (\pm 14 days)

- ADAS-cog.
- C-SSRS.
- Review and record new concomitant medications.
- Assess symptoms/adverse events by asking the participants to respond to a non-leading question such as “How have you been feeling?”
- Brief physical and neurologic examination.
- Vital signs: blood pressure and pulse rate.
- Drug accountability. Any discrepancies are recorded in the source and the subject and caregiver/informant are counseled regarding proper dosing compliance.
- Dispense study drug. Subjects take their dose of study medication in the clinic.

6.1.3 Month 6 (\pm 14 days)

- ADAS-cog, MMSE, CDR, ADCS-ADL, COWAT, CFT, Trail making test (Versions A and B), NPI, RUD Lite and DEMQOL- proxy.
- C-SSRS.
- Review and record new concomitant medications.
- Assess symptoms/adverse events and by asking the participants to respond to a non-leading question such as “How have you been feeling?”
- Brief physical and neurologic examination.
- Body weight.
- ECG.
- Vital signs: blood pressure and pulse rate.
- Blood sampling for safety laboratory testing including HbA1c.
- Collect blood samples for PK and PD.

- Drug accountability. Any discrepancies are recorded in the source and the subject and caregiver/informant are counseled regarding proper dosing compliance.
- Dispense study drug. Subjects take their dose of study medication in the clinic.

6.1.4 Month 9 (\pm 14 days)

- ADAS-cog.
- C-SSRS.
- Review and record new concomitant medications.
- Assess symptoms/adverse events and by asking the participants to respond to a non-leading question such as “How have you been feeling?”
- Brief physical and neurologic examination.
- Vital signs: blood pressure and pulse rate.
- Drug accountability. Any discrepancies are recorded in the source and the subject and caregiver/informant are counseled regarding proper dosing compliance.
- Dispense study drug. Subjects take their dose of study medication in the clinic.

6.1.5 Month 12 (\pm 14 days)

- ADAS-cog, MMSE, CDR, ADCS-ADL, COWAT, CFT, Trail making test (Versions A and B), NPI, RUD Lite and DEMQOL- proxy.
- C-SSRS.
- Review and record new concomitant medications.
- Assess symptoms/adverse events and by asking the participants to respond to a non-leading question such as “How have you been feeling?”
- Brief physical and neurologic examination.
- Body weight.
- ECG.

- Vital signs: blood pressure and pulse rate.
- Blood sampling for safety laboratory testing including HbA1c.
- Collect blood samples for PK and PD.
- Drug accountability. Any discrepancies are recorded in the source and the subject and caregiver/informant are counseled regarding proper dosing compliance.
- Dispense study drug. Subjects take their dose of study medication in the clinic.

6.1.6 Month 15 (\pm 14 days)

- C-SSRS.
- Review and record new concomitant medications.
- Assess symptoms/adverse events and by asking the participants to respond to a non-leading question such as “How have you been feeling?”
- Brief physical and neurologic examination.
- Vital signs: blood pressure and pulse rate.
- Drug accountability. Any discrepancies are recorded in the source and the subject and caregiver/informant are counseled regarding proper dosing compliance.
- Dispense study drug. Subjects take their dose of study medication in the clinic.

6.1.7 Month 18 (\pm 14 days)

- ADAS-cog, MMSE, CDR, ADCS-ADL, COWAT, CFT, Trail making test (Versions A and B), NPI, RUD Lite and DEMQOL- proxy.
- C-SSRS.
- Review and record new concomitant medications.
- Assess symptoms/adverse events and by asking the participants to respond to a non-leading question such as “How have you been feeling?”
- Brief physical and neurologic examination.

- Body weight.
- ECG.
- Vital signs: blood pressure and pulse rate.
- Blood sampling for safety laboratory testing including HbA1c.
- Collect blood samples for PK and PD.
- Drug accountability. Any discrepancies are recorded in the source and the subject and caregiver/informant are counseled regarding proper dosing compliance.
- Dispense study drug. Subjects take their dose of study medication in the clinic.

6.1.8 Month 21 (\pm 14 days)

- C-SSRS.
- Review and record new concomitant medications.
- Assess symptoms/adverse events and by asking the participants to respond to a non-leading question such as “How have you been feeling?”
- Brief physical and neurologic examination.
- Vital signs: blood pressure and pulse rate.
- Drug accountability. Any discrepancies are recorded in the source and the subject and caregiver/informant are counseled regarding proper dosing compliance.
- Dispense study drug. Subjects take their dose of study medication in the clinic.

6.1.9 Month 24 (\pm 14 days)

- ADAS-cog, MMSE, CDR, ADCS-ADL, COWAT, CFT, Trail making test (Versions A and B), NPI, RUD Lite and DEMQOL- proxy.
- C-SSRS.
- Review and record new concomitant medications.

- Assess symptoms/adverse events and by asking the participants to respond to a non-leading question such as “How have you been feeling?”
- Brief physical and neurologic examination.
- Body weight.
- ECG.
- Vital signs: blood pressure and pulse rate.
- Blood sampling for safety laboratory testing including HbA1c.
- Collect blood samples for PK and PD.
- Drug accountability. Any discrepancies are recorded in the source.
- End of study procedures

6.2 EARLY TERMINATION

In the event a subject discontinues participation prior to completion of the Month 24 visit the following procedures should be performed.

- ADAS-cog, MMSE, CDR, ADCS-ADL, COWAT, CFT, Trail Making Tests (Versions A and B), NPI, RUD Lite and DEMQOL- proxy.
- C-SSRS.
- Review and record new concomitant medications.
- Assess symptoms/adverse events and by asking the participants to respond to a non-leading question such as “How have you been feeling?”
- Brief physical and neurologic examination.
- Body weight.
- ECG.
- Vital signs: blood pressure and pulse rate.
- Blood sampling for safety laboratory testing including HbA1c.
- Collect blood samples for PK and PD.
- Drug accountability. Any discrepancies are recorded in the source.

6.3 SUBJECT WITHDRAWAL

Participants may withdraw from the study at any time at their own request or the request of their study partner, caregiver/informant/guardian, or they may be withdrawn at any time at the discretion of the Investigator or Sponsor for safety, behavioral, compliance, or administrative reasons. If a participant does not return for a scheduled visit, every effort should be made to contact the participant including certified letter, return receipt requested. The investigator should inquire about the reason for withdrawal, request that the participant return all unused investigational product(s), request that the participant return for a final visit, if applicable, and follow-up with the participant regarding any unresolved adverse events.

If the participant withdraws from the study, and also withdraws consent for disclosure of future information, no further evaluations should be performed, and no additional data should be collected. The Sponsor may retain and continue to use any data collected before such withdrawal of consent. An individual patient enrolled in the trial may be discontinued from dosing based on a specific adverse event profile as recommended by the Sponsor in discussions with the PI. The Sponsor may temporarily stop dosing of enrolled subjects and/or additional enrollment of new patients at any time, and may permanently terminate the study at any time.

Any emergent medical condition or safety finding that, in the opinion of the Investigator, may jeopardize the participant's safety if he/she continues in the study will be sufficient reason for participant discontinuation from the study. The participant should be followed as indicated for the AE until resolved, declared stable or the participant is lost to follow up. Safety data will be obtained from the physical and neurological examination, vital signs, routine laboratory tests, ECG, and neuropsychological testing batteries.

7.0 ASSESSMENTS

7.1 SAFETY AND TOLERABILITY

7.1.1 Vital Signs

Vital signs measurements will consist of blood pressure and pulse rate while the participant is in a sitting or supine position. Vital signs will be conducted in the same position (sitting or supine) at all the study visits and position captured in the source documentation. Participants should be sitting or supine at least 5 minutes prior to vital signs determination.

7.1.2 Electrocardiogram

12-lead ECG should be recorded after participants have been resting at least 5 minutes in the supine position. Each original recording will be evaluated by the PI or designee following the measurement. The interpretation of results will follow the categories “normal,” “abnormal, NCS,” or “abnormal, CS”. An abnormal measurement may be repeated at the PI or designee discretion. If the abnormal ECG measurements are considered as clinical significant, the abnormality will be recorded as AE in the eCRF.

When assessing eligibility at the Baseline visit, the presence of BBB (either left or right) is allowable as long as the absolute QTcF value does not exceed 500 ms and the subject does not have any other cardiac exclusions as described in exclusion criterion 4. When an ECG displays a paced rhythm indicating a functioning pacemaker is present, there is no upper limit as long as there are no related cardiac exclusions. Note. If there is no known history of BBB (either right or left), the discovery of such should prompt further investigation prior to proceeding with screening.

At the Baseline visit, the participant’s TTP488-301 Month 18 ECG will be reviewed locally in order to verify continued eligibility for the study. If the QTcF is >480 msec based on the local QTcF reading, the participant is not eligible. If the QTcF represents an increase from TTP488-301 Baseline of > 45 msec, the participant is not eligible.

At any time during the study, a subject with an absolute QT > 480 msec or an increase from baseline in QTcF > 45 msec should prompt a call to the Sponsor’s medical monitor for guidance on how to proceed.

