1.5 Study Design

This is an open-label extension study in patients with mild Alzheimer's disease who have successfully completed participation in the azeliragon Phase 3 TTP488-301 (STEADFAST) trial. Patients may receive azeliragon 5 mg/day for up to 2 years.

Participants were required to continue to be on SoC of a stable background acetylcholinesterase inhibitor therapy and / or memantine and continue the therapy for the duration of the trial, unless the investigator judges that the dose needs to be reduced or stopped due to a safety and/or tolerability reason.

Subjects were expected to participate in approximately 9 outpatient visits including baseline which is the same visit at the Month 18 visit in the TTP488-301 study.

Protocol TTP488-301 included two studies with a common infrastructure (A-study and B-study). Participants from either study are allowed to roll over into this open-label extension study.

A-study is conducted at multiple sites in the US and Canada. B-study is conducted at multiple sites in the US, Canada, Ireland, UK, South Africa, New Zealand, and Australia.

This study was terminated prematurely before participation outside of the US and Canada began; therefore, this study is conducted at multiple sites in the US and Canada.

The overall structure of the study includes the following periods:

Baseline Study Period: (Month 18 visit of TTP488-301): At the Month 18 visit of TTP488-301, subjects who met eligibility requirements were offered enrollment into this open-label extension study. Subjects had baseline assessments for efficacy and safety measures, including PK assessments.

Treatment Period: (Day 1 (Month 18 visit of TTP488-301) — Month 24): Subjects were treated with open-label azeliragon 5 mg QD. Efficacy and safety measures were taken. Blood samples were taken and subjects have assessments for safety and PK.

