5.3.5 Electrocardiography

The heart rate, QT, PR, and QRS intervals will be recorded at each assessment time. No formal inferential statistics will be applied to the ECG data.

For each post-Baseline assessment, descriptive statistics are provided for the assessment value and the change from Baseline to the assessment with mean, median, standard deviation, minimum, and maximum at each assessment time.

In addition, the number of subjects with corrected and uncorrected QT values >500 msec will be summarized. Values from individual tracings within the triplicate measurement on Day 1, time 0 hour that are >500 msec will not be included in the categorical analysis unless the average from that triplicate measurement is also >500 msec.

Electrocardiography data will be summarized by Baseline and Change from Baseline to each scheduled assessment time with descriptive statistics.

Corrections to QT intervals will be made by Fridericia's method (QTcF). Categorical analysis will be done consistent with ICH E14, "Clinical evaluation of QT/QTc interval prolongation and proarrhythmic potential for non-antiarrhythmic drugs" (October 2005).

In accordance with ICH E14, subjects will be categorized and summarized as described above according to:

- Absolute QTc interval prolongation:
 - QTc interval > 450
 - QTc interval > 480
 - QTc interval > 500
- Change from Baseline in QTc interval:
 - QTc interval increases from Baseline > 30
 - QTc interval increases from Baseline > 60.

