6.6 Values Below LLQ

Concentrations for TTP488 below the lower limit of quantification (LLQ) for the assay will be set to zero for the purpose of analysis.

7 Analysis Deviations

All statistical analyses and summary information will be generated according to this analysis plan. Any deviation from this plan will be documented in the clinical study report. Exploratory analyses are permitted per protocol; those analyses will not be considered to be deviations.

8 Software

All analyses will be done using SAS Version 9.4 or later.

9 Data Displays

The plans for displaying data will be appropriate for open-label extension studies.

Planned displays will include, but are not limited to, the following:

- Summary of Accountability (number enrolled, completing, withdrawn, by reason; listing of withdrawals with study day and reason)
- Summary of Demography and Background Data
- Summary of Adverse Events
- Summary of Adverse Events by severity and by relatedness
- Summary of Vital Signs (change over time; criteria of potential clinical concern)
- Summary of Laboratory Data, including LFTs (change over time, TEAV, and criteria of potential clinical concern)
- Summary of PK Data
- Summary of PD Data
- Summary of Efficacy Data (ADAS-cog, CDR-sb, CDR-global, MMSE, ADCS-ADL, NPI)
- Listing of Demography
- Listing of Dosing
- Listing of all Adverse Events
- Listing of all Adverse Events that resulted in Death
- Listing of all Serious Adverse Events
- Listing of all Adverse Events resulting in Study Termination
- Listing of Treatment-emergent Abnormal Values of Potential Clinical Concern for Clinical Laboratory Data
- Listing of Vital Signs Data
- Listing of QTc data that meet criteria of potential concern as described in ICH E14
- Listing of azeliragon, TTP1494, TTP2266, TTP2123 Concentration Data
- Listing of plasma A β (total, 1-40 and 1-42)

In addition to the data summaries and listings described above, the set of displays will include clinical laboratory normal ranges (with units) and also a display of the MedDRA mapping glossary, which will display the verbatim text as reported by the investigator, the LLT, PT, and SOC.

10 Values of Potential Clinical Concern

Parameter	Threshold (study-specific threshold calculated)
Hematology	
Hemoglobin	<8.5 g/dL
Hematocrit	<25 %
WBC (Leukocytes)	<0.6 x LLN (<2.1 10 ³ /uL)
Platelets	<0.5 x LLN (<70 10 ³ /uL)
Total Neutrophils (Abs)	<0.8 x LLN (<0.8 10 ³ /uL)
Lymphocytes (Abs)	<0.6 x LLN (<0.6 10 ³ /uL)
Chemistry	

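### The on-study ECG alert sets its absolute 480 msec limit on uncorrected QT, so QTcF can exceed 480 with no call prompted when heart rate is above 60 bpm and baseline QTcF is above 435 msec

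*Protocol*

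**What the plan says.** Protocol 7.1.2 gives the on-study rule: "a subject with an absolute QT > 480 msec or an increase from baseline in QTcF > 45 msec should prompt a call". The person called is the sponsor's medical monitor, who then advises the site. One sentence therefore uses two quantities: uncorrected QT for the absolute limit and QTcF for the change limit.

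The entry rules use QTcF for both. The eligibility paragraph of the same section says "If the QTcF is >480 msec based on the local QTcF reading, the participant is not eligible", and exclusion criterion 3 in Protocol 4.2 bars "Subjects demonstrating a QTcF > 480 msec or a >45 msec increase from the TTP488-301 Baseline value". Known bundle branch block is allowed up to a QTcF of 500, and a paced rhythm has no upper limit.

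Other ECG review exists. Under Protocol 7.1.2, "Each original recording will be evaluated by the PI or designee following the measurement"; an abnormal tracing may be repeated, and a clinically significant abnormality is recorded as an adverse event. In the analysis, SAP 5.3.5 corrects by Fridericia's method, counts QTc above 450, 480 and 500, and states that "the number of subjects with corrected and uncorrected QT values >500 msec will be summarized".

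**The concern.** The alert brings a possible QT signal in one subject to the medical monitor while that subject is still being dosed. Uncorrected QT shortens as heart rate rises, so above 60 bpm a fixed QT limit corresponds to a QTcF limit higher than its face value. A subject could then pass the QTcF level that bars ordinary entry, and even 500 msec, without meeting either limit.

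ECG is among the primary endpoints (Protocol 2.2), and scheduled on-study tracings come only at Months 6, 12, 18 and 24 or at early termination. A tracing that prompts no call could be followed by about six months of daily dosing before the next scheduled one. At stake is individual safety monitoring, not the validity of any analysis.

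**Working it through.** The plan has no figure of its own to reproduce here. The check converts the alert into QTcF terms.

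**Inputs**
- Call prompted if QT > 480 msec, or if QTcF rises > 45 msec from baseline (Protocol 7.1.2).
- Highest ordinary entry QTcF: 480 msec (Protocol 4.2 and 7.1.2).
- Baseline: last value before the first open-label dose (Protocol 9.0; SAP 6.1 for safety).
- Correction: Fridericia (SAP 5.3.5), QTcF = QT / RR^(1/3), with RR = 60/HR in seconds.
- Heart rates are assumed, because the documents give none.

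**Step 1. What QT 480 means as QTcF.** 480 / (60/HR)^(1/3) gives 480.0 at 60 bpm, 493.0 at 65, 505.3 at 70, 517.1 at 75 and 528.3 at 80. At or below 60 bpm QTcF does not exceed QT, so any QTcF above 480 already meets the QT limit and there is no gap.

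**Step 2. Add the change limit.** No call is prompted when QT ≤ 480 and the QTcF rise is ≤ 45. The highest QTcF with no call is therefore min(480 / RR^(1/3), baseline + 45). It can exceed 480 only if baseline > 480 − 45 = 435 and heart rate > 60 bpm.

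Highest QTcF (msec) with no call:

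| Baseline QTcF | 60 bpm | 65 bpm | 70 bpm | 75 bpm | 80 bpm |
|---|---|---|---|---|---|
| 435 | 480 | 480 | 480 | 480 | 480 |
| 440 | 480 | 485 | 485 | 485 | 485 |
| 455 | 480 | 493.0 | 500 | 500 | 500 |
| 460 | 480 | 493.0 | 505 | 505 | 505 |
| 480 | 480 | 493.0 | 505.3 | 517.1 | 525 |

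**Step 3. Where the marks fall.** The heart rate at which QT 480 equals a given QTcF is 60 × (QTcF/480)^3: 67.8 bpm for QTcF 500 and 78.5 bpm for 525. Passing 500 unprompted needs a baseline above 455 (500 − 45) and a rate above about 68 bpm. The ceiling of 525 (480 + 45) applies from about 79 bpm.

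**Step 4. An example.** Baseline QTcF 470 rises to 510, a rise of 40. The QT is 463.4 at 80 bpm and 473.4 at 75, so neither limit is met. At 70 bpm the QT is 484.5 and a call is prompted.

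**Step 5. Test the repair.** Compare the present rule with a rule that fires on QT or QTcF > 480, keeping the change limit:

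| Case | Present rule | QT or QTcF |
|---|---|---|
| QTcF 510 at 80 bpm, baseline 470 | no call | call |
| Bundle branch block, QT 485 at 62 bpm (QTcF 490.3) | call | call |
| QT 505 at 50 bpm (QTcF 475.2) | call | call |
| QTcF 490 at 65 bpm (QT 477.1), no rise | no call | call |

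Under the repaired rule no QTcF above 480 goes unprompted at any heart rate, and no existing trigger is lost.

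**The case against.** The strongest reply is that this is a wording slip. Wherever else the protocol gives an absolute ECG limit it means QTcF, and the pair 480 and 45 mirrors the QTcF entry pair in the preceding paragraph. Sites that read it that way have no gap. This may well be right about intent, but the operative sentence distinguishes QT from QTcF and nothing in the documents corrects it.

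Other points limit the weight:
- The text says a call should be prompted, for guidance. It is not a stopping rule.
- The investigator judges every tracing and can discontinue a subject for any safety finding (Protocol 6.3). The IDMC reviews safety data (Protocol 9.6), and medically qualified staff review ECG listings (SAP 4.2). None of these sets a QTcF value that prompts a call during treatment.
- The entry limit is not uniform, and no rule says an on-study trigger must equal it. That is true. Even so, the present rule can pass the 500 msec allowed for bundle branch block.
- The alert says only baseline, without saying which. Protocol 9.0 and SAP 6.1 favour the open-label baseline; if the TTP488-301 Baseline were meant, the same 435 cut-off would apply to that value.
- The SAP says "This study was terminated prematurely before participation outside of the US and Canada began", so an amendment may come too late. This changes the remedy but not the finding.

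**Conclusion.** The concern holds as a bounded safety-monitoring defect that should be corrected. The absolute limit is on the wrong quantity, and the gap exists exactly when heart rate exceeds 60 bpm and baseline QTcF exceeds 435 msec. At the highest ordinary baseline of 480, the unprompted QTcF reaches 493 at 65 bpm, 505 at 70 and 517 at 75, with a ceiling of 525 from about 79 bpm. With a baseline of 440 the ceiling is 485.

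This rests on a literal reading of QT, Fridericia's correction, the open-label baseline, and subjects without bundle branch block or pacing. How many subjects fall in the gap cannot be computed. The planned QTc analyses are not affected.

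**What to change.** In the last paragraph of Protocol 7.1.2, make the absolute trigger *QT or QTcF > 480 msec*. Leave the change limit as it is, and add no exemption for bundle branch block or pacing. Replacing QT by QTcF alone would also close the gap, but it would drop triggers at slow heart rates, such as QT 505 at 50 bpm when the QTcF rise is 45 msec or less.

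The cost is two added words in an amendment, IRB/REB review and a memo to sites. No new measurement is needed: SAP 5.3.5 says "The heart rate, QT, PR, and QRS intervals will be recorded at each assessment time", and the change limit already requires QTcF. There would be somewhat more calls above 60 bpm, including repeated calls for bundle branch block or paced subjects who entered above a QTcF of 480. Calls at or below 60 bpm would not change, and the SAP needs no edit.

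If dosing has ended, skip the amendment. Use the display planned in SAP Section 9, "Listing of QTc data that meet criteria of potential concern as described in ICH E14", to identify on-study tracings with QTcF > 480 and QT ≤ 480. The only cost is that check.
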